7.1.2 Serious Adverse Events

A serious AE is one that:

- led to death,
- led to serious deterioration in the health of a subject that:
 - resulted in a life-threatening illness or injury,
 - resulted in permanent impairment of a body structure or body function,
 - required inpatient hospitalization or prolongation of existing hospitalization,

- resulted in medical or surgical intervention to prevent permanent impairment to a body structure or a body function, or
- led to fetal distress, fetal death or a congenital anomaly or birth defect.

The following clarifications are provided for the serious AEs:

- Life-threatening means that the subject was, in the view of the investigator, at immediate risk of death from the event as it occurred. The definition does not include an event that, had it occurred in a more severe form, might have caused death.
- Hospitalization for elective treatment of a pre-existing condition that did not worsen during the study is not considered a serious AE.
- "Inpatient" hospitalization means the subject has been formally admitted to a hospital for medical reasons. This may or may not be overnight. It does not include presentation at a causality or emergency room.
- Important medical events that may not result in death, or be lifethreatening, however based upon appropriate medical judgment, may jeopardize the subject and may require medical or surgical intervention to prevent one of the outcomes listed in this definition.
- It is significant for any other reason.

7.1.3 Anticipated Adverse Events:

Anticipated AEs are those events that are reasonably expected to occur as a result of the subject's disease state or treatment. For this study, anticipated AEs associated with the procedure or post-procedure include, but are not limited to, the following;

- 1. Infections, both deep and superficial.
- 2. Allergies and other reactions to device materials.
- 3. Hematoma.
- 4. Arthraglia
- 5. Joint stiffness
- 6. Joint effusion
- 7. Joint swelling
- 8. Joint warmth
- 9. Injection site pain
- 10. Blood vessel damage
- 11. Nerve damage
- 12. Arthritis
- 13. Arthropathy
- 14. Gait disturbance

7.1.4 Unanticipated Adverse Device Events

An Unanticipated Adverse Device Effect (UADE) is defined as any serious AE on the study subject's health or safety, or any life-threatening problem or death caused by or associated with the treatment, if, the effect, problem or death was not previously identified in this Investigational Plan or Instructions for Use in its nature, frequency, or severity. UADEs may also include other serious problems associated with the treatment that affect the rights or welfare of study subjects.

7.2 Adverse Event Documentation

AE information will be collected on all subjects. All AEs must be reported in the source documents and in the Electronic Data Collection (EDC) database. AEs will be evaluated by the investigator and differentiated by:

- Serious, as defined in Section 8.1.2
- Severity of the event, defined as:
 - Mild: Awareness of signs and symptoms, but easily tolerated; are of minor irritant type, causing no loss of time from normal activities; symptoms would not require medication or a medical evaluation; signs and symptoms are transient.
 - Moderate: Discomfort severe enough to cause interference with usual activities; requiring treatment, but not extended hospitalization or intensive care for the subject.
 - Severe: Incapacitating with inability to do work or usual activities; signs and symptoms may be systemic in nature or require medical evaluation and/or treatment; requiring additional hospitalization or intensive care (prolonged hospitalization).
- Relatedness to the device or procedure, defined as:
 - Unrelated: AE is due to the underlying disease state or concomitant medication or therapy not related to the study-specific treatment or procedures.
 - Probably not Related: AE had minimum or no temporal relationship to the study-specific treatment or procedures and/or more likely alternative etiology exists.
 - Possibly Related: AE had a strong temporal relationship to the studyspecific devices or procedures and alternative etiology is equally or less likely compared to the potential relationship to the study-specific treatment or procedures.
 - Probably Related: AE had a strong temporal relationship to the studyspecific treatment or procedures and another etiology is unlikely.
• Unknown: Relationship of the AE to the study-specific devices or procedures and alternative etiology is unknown.

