7.5 Safety Monitoring

As the study sponsor of this clinical study, Arthrex Inc. will be responsible to monitor it for safety. In the circumstance where UADEs or serious AEs occur due to a procedure, Arthrex, Inc., will convene a review committee which will determine any unreasonable risk to subjects or if the study should be reviewed for modification or early termination.

8 Statistical Method and Sample Size Calculation

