8.7 Safety Endpoints

The primary safety endpoints for this study are based on adverse events. Details regarding analyses of adverse events are provided below. Briefly, adverse event endpoints will include, but are not limited to, the following patient specific endpoints:

- Any adverse event (per patient)
- Any treatment related AE
- Any serious AE
- Any serious AE that is treatment related
- Patient death

Specific endpoints such discomfort and pain, erythema, swelling, bruising, hemorrhage, and papules will be compared between treatment groups in terms of both per patient incidence rates and total counts. Fisher's exacts tests will be used to provide descriptive comparisons between incidence rates. Counts of AEs will be displayed overall and over time.

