8.8 Safety Analysis

Assessment of safety will be based primarily on the incidence and severity of complications and adverse reactions associated with the treatment. Adverse event rates will be summarized by type of AE and for specific AEs in two ways: 1) per patient using counts and percentages and 2) by event, summarizing event counts by visit interval over time. Treatment and procedure related events will be summarized by severity. Events listings will be provided that include details such as relatedness, severity, onset and resolution status will be provide for all events and for relevant subsets of events such as serious events and related events. All safety endpoints will be summarized separately for investigational and control groups. Incidence rates for grouped and individual adverse events will be compared using counts, percentages, and descriptive Fisher's exact test nominal p-values. Grouped adverse events will include events at least possibly related to study treatment and serious adverse events.

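### The relatedness scale leaves intermediate-timing events without a graded category, and the plan does not say that Unknown counts as related, so related-event summaries lean low

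*Combined protocol and SAP*

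**What the plan says.** Section 7.2 asks the investigator to rate each adverse event as Unrelated, Probably not Related, Possibly Related, Probably Related or Unknown.

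- The test for Possibly Related reads "AE had a strong temporal relationship to the studyspecific devices or procedures and alternative etiology is equally or less likely"; the comparison is with a link to the study intervention. Probably Related also requires a strong temporal link, with any other cause unlikely.
- One step lower, the test for Probably not Related is met by little or no temporal link, by a likelier other cause, or by both.
- The fifth category, Unknown, is worded as "Relationship of the AE to the study-specific devices or procedures and alternative etiology is unknown".

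The analysis sections use relatedness in three ways:

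- Section 8.7 Safety Endpoints lists "Any treatment related AE" and a matching endpoint for serious events, with no mapping to the five categories.
- Section 8.8 Safety Analysis states: "Grouped adverse events will include events at least possibly related to study treatment and serious adverse events". It also summarizes related events by severity.
- Section 8.9.1 plans a listing of events with a *definite* relationship, which is not a category in 7.2.

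Section 7.5, repeated in substance in 9.2, sets the sponsor's committee trigger: "In the circumstance where UADEs or serious AEs occur due to a procedure, Arthrex, Inc., will convene a review committee".

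For severity, 7.2 describes Moderate as interference with usual activities that needs treatment but not extended hospital or intensive care. Severe opens with incapacitation and ends with a clause on additional hospitalization or intensive care. Semicolons separate the Severe elements, and the text does not say whether all are required.

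**The concern.** Adverse events are the basis of the primary safety endpoints, and the related-event rate is one of the main figures a reader takes from them. If a plausible class of events can be placed only in Unknown, and Unknown is not counted as related, that rate is understated by a rule that nobody chose deliberately. Knee swelling first reported between the last injection at Week 2 and the 2-month visit is a realistic example, since joint swelling and effusion are on the anticipated list in 7.1.3. Leaving the rule open also means that an analyst may have to settle it once the data are in hand.

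Two neighbouring definitions have the same weakness. The causal wording of the committee trigger does not match the relatedness scale, and the severity grades can overlap.

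**Working it through.** No figure in the plan bears on this point, so the check applies the definitions as rules.

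**1. Which category takes an event with intermediate timing and no better explanation?**

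| Category (7.2) | Requirement | Met? |
|---|---|---|
| Unrelated | Due to underlying disease or to unrelated medication or therapy | No |
| Probably not Related | Minimum or no temporal link, and/or a likelier cause | No, on either limb |
| Possibly Related | Strong temporal link, and alternative no more likely | Fails on timing |
| Probably Related | Strong temporal link, and alternative unlikely | Fails on timing |
| Unknown | Relationship and alternative cause both unknown | Available, not compelled |

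None of the four graded categories fits as worded.

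**2. Is Unknown at least possibly related?** Read by label, the group is Possibly and Probably, two of the five categories, and Unknown is out. Read by position in the list (third or later), it would be Possibly, Probably and Unknown, and Unknown is in. The label reading is the natural one, but no rule fixes it. The causality codes on the adverse event form in Appendix 2-6 are too garbled in the available text to settle it.

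**3. Where does an Unknown event appear?**

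| Output | Unknown event counted? |
|---|---|
| Any AE (8.7 Safety Endpoints) | Yes |
| Any serious AE (8.7); serious group (8.8 Safety Analysis) | Yes, if serious |
| Related AE and related serious AE (8.7) | Not on plain wording |
| At-least-possibly-related group; severity summary of related events (8.8) | Not on plain wording |
| Severe treatment-related listing (8.9.1) | Not on plain wording |
| *Definite* listing (8.9.1) | Cannot be determined; no such category in 7.2 |
| All-event listings (8.8, 8.9.1) | Yes |

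**4. Committee trigger.** Three causal standards stand side by side. Section 7.2 rates relatedness to the device or the procedure. Section 7.1.4 defines an unanticipated device effect through causation by, or association with, the treatment. Sections 7.5 and 9.2 speak of serious events due to a procedure. The trigger does not refer to the 7.2 ratings, so the handling of a serious event rated Unknown, or attributed to the device, is unstated.

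**5. Severity.** Take an event that is incapacitating, treated and not hospitalized. If every Severe element is required, it is not Severe; if one is enough, it is. It also satisfies Moderate if incapacitation is taken as a form of interference. The same event can therefore be graded either way.

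**The case against.** The best reply is that nothing expressly excludes Unknown. The words strong and minimum carry no numeric limits, so an investigator may place an intermediate event in an adjacent category, and Unknown strictly requires that the alternative cause be unknown too. Unknown events stay visible in the any-AE and all-event outputs, so regrouping them is easy. The comparisons use descriptive Fisher tests, and no between-arm bias has been shown. All of this stands, and it limits the point. It does not answer the gap in the definitions or the missing counting rule.

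A reader might go further and infer that an Unknown rating lets a serious event bypass the only sponsor-level safety review, or excludes it from the committee trigger. The documents do not support either inference. Under 7.3 all serious events go to the sponsor or designee within 24 hours and the monitor evaluates every one, whatever the relatedness. The trigger is not tied to the investigator's rating. An event on the anticipated list can still be an unanticipated device effect through its frequency or severity (7.1.4).

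A reader might also infer that incapacitating reactions treated without hospitalization will be graded Moderate. That follows only if every Severe element is mandatory. Incapacitation is the lead Severe criterion, and such an event meets it.

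**Conclusion.** The concern holds for relatedness. As worded, 7.2 gives no graded category to an event with intermediate timing and no better explanation. On the plain reading of 8.7 Safety Endpoints and 8.8 Safety Analysis, events rated Unknown are left out of the related-AE and related-SAE summaries. The direction is toward fewer related events. The size depends on how often Unknown is used, which the documents do not give, so no figure is offered. The conclusion rests on reading the group by label and on some investigators using Unknown for such events.

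The committee trigger and the severity grades are open points of wording. For both, the handling is undefined; the text shows neither an exclusion nor a systematic downgrade. Efficacy testing is not affected.

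**What to change.** 1. State that Unknown counts as related in every related-event endpoint, summary and listing.
2. In Possibly Related, replace the strong temporal relationship with a plausible one, so that intermediate timing has a graded category.
3. Align the related-event listing in 8.9.1 with the 7.2 scale, since *definite* is not one of its categories.
4. Reconcile the causal wording of the committee trigger in 7.5 and 9.2 with 7.2 and 7.1.4, so that a serious event rated Unknown or attributed to the device is not left open.
5. State in 7.2 whether any one Severe element is enough. A redesign of the severity scale is not needed.

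The cost is wording in the protocol and analysis sections, with matching instructions for the adverse event form. The downside is a slightly higher reported related-AE rate.

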7.3 Adverse Event and Unanticipated Adverse Device Effect Reporting

At every subject encounter, the investigator will determine if there has been an adverse event since the last encounter.

For this study, serious adverse events must be reported to Arthrex or designee within 24 hours of event discovery by the site and entered into the EDC database. At the time of the initial report, the outcome (resolution status) may not be known. Updated information must be entered into the EDC database until final resolution of the event.

UADEs must also be reported by the investigator to the approving IRB as soon as possible, but not later than 10 working days after the investigator first learns of the effect. The sponsor must report to the FDA, all reviewing IRBs, and participating investigators within 10 working days of notification from the investigator of a UADE.

The monitor will provide medical surveillance on adverse events and will evaluate all Serious Adverse Events (SAEs)

7.4 **Device Complications**

For this study all device malfunctions including ; unable to pull up outer syringe, unable to pull up inner syringe, damaged parts, cracked parts, packaging – device/component missing, packaging – broken in package, leaking, air mixed with blood, piece broke from device , frozen or other will be collected and reported on associated eCRF.

7.5 Safety Monitoring

As the study sponsor of this clinical study, Arthrex Inc. will be responsible to monitor it for safety. In the circumstance where UADEs or serious AEs occur due to a procedure, Arthrex, Inc., will convene a review committee which will determine any unreasonable risk to subjects or if the study should be reviewed for modification or early termination.

8 Statistical Method and Sample Size Calculation

8.1 Primary Effectiveness Hypothesis for Pain

The primary effectiveness hypothesis for this study is that ACP treatment is superior to control in terms of mean change from baseline to Month 6 in the WOMAC Pain score. Symbolically, the null and alternative hypotheses may be expressed as follows:

Ho: $\delta(\text{pain})_{ACP} - \delta(\text{pain})_{Control} \leq 0$

Ha: $\delta(\text{pain})_{ACP} - \delta(\text{pain})_{Control} > 0$

Where $\delta(pain)_{ACP}$ and $\delta(pain)_{Control}$ are the expected mean changes from baseline to Month 6 in the WOMAC Pain score among patients in the ACP and control groups, respectively.

8.2 Conditional Effectiveness Hypothesis for Function

The study is designed to permit an additional labeling claim beyond reduction in pain while maintaining control of type 1 error. The additional labeling claim concerns improvement in patient function. This will be measured using change from baseline to Month 6 in the WOMAC Function score. In order to control type 1 error for this study, these two hypotheses were hierarchically specified. First, the primary endpoint concerning WOMAC pain will be tested. If the 1-sided p-value ≤ 0.025 , it will be concluded that the investigational treatment is superior to control in terms of pain reduction and the study will be considered as having met its Study Success criterion. In this case, additionally, the treatment group difference in mean change from baseline to Month 6 will also be tested for the WOMAC Function score using a 1-sided p-value ≤ 0.025 . Testing of the conditional endpoint is contingent on demonstrating superiority in terms of WOMAC Pain and it is not intended to require superiority in both WOMAC Pain and WOMAC Function for Study Success.

The conditional effectiveness hypothesis for this study is that ACP treatment is superior to control in terms of mean change from baseline to Month 6 in the WOMAC Function score. Symbolically, the null and alternative hypotheses may be expressed as follows:

```
Ho: \delta(\text{function})_{ACP} - \delta(\text{function})_{Control} \le 0
Ha: \delta(\text{function})_{ACP} - \delta(\text{function})_{Control} > 0
```

Where $\delta(function)_{ACP}$ and $\delta(function)_{Control}$ are the expected mean changes from baseline to Month 6 in the WOMAC Function score among patients in the ACP and control groups, respectively.

Formal testing of the conditional endpoint will only take place if the null hypothesis involving the primary endpoint is rejected at 1-sided alpha=0.025. In that case, the null hypothesis concerning the conditional endpoint will be tested, also at 1-sided alpha=0.025. By structuring the hypothesis testing hierarchically and by the 'closed testing principle' no multiplicity adjustment is necessary.

8.3 Statistical Methods for Testing Superiority

8.3.1 MMRM

Superiority testing will be performed using a mixed model for repeated measures (MMRM) analysis of covariance (ANCOVA) Model.³⁹ The MMRM approach is a direct likelihood approach requiring specialized statistical software. For this study, all MMRM parameters will be estimated using SAS PROC MIXED. The MMRM model is notable for its inclusion of all available data from all eligible subjects and does not require their exclusion as in complete case analysis or arbitrary assignment of some value as in Last Observation Carried Forward (LOCF). Inclusion of outcome data from time points earlier than Months 6 informs the implicit imputation of missing Month 6 values through the covariance matric used to model the random effects.

The random effects in the MMRM model will based on the so-called 'unstructured covariance matrix' in which variances over time are allowed to vary as are the pair-wise correlations over time.

The values over time will include all WOMAC scores, namely at each of the 3 follow-up time points, visit 5 / 2 months, visit 6 / 3 months, and visit 7 / 6 months.

All WOMAC values will be included in the analysis even if they are obtained outof-window. However, the fraction of out-of-window visits will be summarized at each time point.

The contrast indicated by the primary hypotheses above, $\delta(pain)_{ACP} - \delta(pain)_{Control}$ will be estimated as the treatment group contrast from baseline to Month 6 in the WOMAC score derived from the MMRM. The null hypothesis is that the true value of this contrast is equal to zero. The same approach will be taken for the WOMAC Function score if superiority in pain relief is demonstrated.

8.3.2 Covariates in MMRM

The MMRM model must contain an indicator variable for treatment group, a categorical time factor, and treatment group by time interaction. It is also necessary to include to the baseline value of the WOMAC outcome variable (either pain or function) so that significance levels will apply equally to values over time and to changes from baseline. Often a factor for site is included in the MMRM to account for randomization within site. Given the modest sample size and in

response to FDA Advisory items c.1.b (dated July 23, 2015), site will not be included in the primary MMRM. Instead, the impact of site heterogeneity on estimated treatment group differences will be evaluated in supporting analyses by introducing an additional random effect as described below.

It is often considered useful to include additional baseline covariates in order to further reduction of potential bias due from missing values. Candidate variables include age, gender, BMI, and prior analgesic use. However, in response to FDA Advisory item c.1.b, these variables will not be included in the primary MMRM model. Instead, additional baseline covariates will be added to the model in exploratory analyses only if any of these variables appear with clinically significant imbalance between treatment groups. The purpose of these analyses would to be determine the extent to which such imbalance impacts on estimated treatment group differences and associated significance levels.

8.3.3 Details Concerning the MMRM

As stated above, the covariance matrix for MMRM is an unstructured covariance matrix in which each of the 3 variances (2 months, 3 months, and 6 months) are free to vary as are the 6 pairwise covariances. That is, the covariance matrix for the MMRM will not inlcude any random effects per se, but accounts for correlations among errors by specifying the form of the covariance matrix. The MMRM employs an unstructured covariance in order to produce inferences that are valid under the so-called 'missing at random' (MAR) assumption which is more generally true than the 'missing completely at random' assumption that is required for validity of analyses restricted to complete cases.

The longitudinal model will be specified as a repeated measures model that expresses the WOMAC score as a linear function of treatment, time, treatment-by-time interaction, and a covariate of the baseline pain measurement.

The model can be mathematically expressed as:

 $Y_i = X_i\beta + e_i$

- Yi is change from baseline to Month 6 in WOMAC Pain or Function scores
- βis a vector of fixed-effect regression parameters which includes:
 - $\circ \mu$, the overall mean
 - \circ θ , the treatment effect
 - \circ τ , a vector of post-baseline time effects
 - \circ **η**, a vector of treatment-by-time interaction effects,
 - $\circ \phi$, a vector of covariate effect parameters that only includes baseline WOMAC score but in general could include additional baseline variable,
- X is a design matrix for the fixed effects, and
- **e** is the error vector with
 - $\circ \quad \mathbf{E}(\mathbf{e}) = \mathbf{0} \text{ and}$

• $Var(e) = \sigma_e^2 V_{unstructured}$.

The specific model to be used may be expressed as:

$$Y = b_{int} + b_{base} + b_T + b_{2M} + b_{3M} + b_{6M} + b_T b_{2M} + b_T b_{3M} + b_T b_{6M}$$

With parameters as explained below.

Parameter	Represents
Y	Change from baseline
b _{int}	Model intercept
b _{base}	Baseline value
b_T	Indicator for Active Treatment
$b_{2M} b_{3M}, b_{6M}$	Indicator for each visit
bтb2м, bтb3м, bтb6м	Indicators allowing varying treatment differences at each visit

From this model estimates of treatment effect at specific visits and specifically at Month 6 difference may be obtained as follows.

 $T_{M6} = b_{int} + b_{base} + b_T + b_T b_{M6}$

 $S_{M6} = b_{int} + b_{base}$

 $\Delta_{M6} = T_{M6} - S_{M6} = b_T + b_T b_{M6}$

Where e.g. T_{M6} and S_{M6} are the expected changes from baseline to Month 6 in the WOMAC scores in the active and sham control groups, respectively, in terms of these model parameters, the superiority hypotheses are:

H₀: $\Delta_{M6} = 0$ H₁: $\Delta_{M6} > 0$ when larger values reflect improvement or

H₀: $\Delta_{M6} = 0$ H₁: $\Delta_{M6} < 0$ when smaller values reflect improvement

The following SAS Proc Mixed statements provides the test for this null hypothisis. The key results is listed among the results provided by the 'slice' option of the LSMEANS statement. One of these will provide the treatment group contrast at Month 6.

proc mixed data=dataset method=ml;

class patid trt time;

model womac_pain = trt time trt*time womac_pain_bl / s chisq;

repeated time / type=un subject=patid; lsmeans trt*time / slice=time; run;

The Month 6 treatment group contrast, the p-value associated with the null hypotheses and 95% two-sided confidence interval will be derived from the MMRM in order to test the superiority hypotheses for the primary endpoint and co-primary endpoints.

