in mean percentage changes so large is likely clinically significant given the known reliability and validity of the WOMAC Pain score.

Randomization will be 2:1 in order to increase precision when characterizing the safety profile of the investigational treatment. We assume a one-sided type 1 error of α =0.025 and a standardized mean difference of 0.80 and determined that a total sample size of N=78 (52 ACP and 26 control) patients are required for 90% power. **This value is increased by 15% to N=90 (60 ACP and 30 control)** to account for potential loss-to-follow-up or other exclusions from the primary effectiveness analysis set.

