8.8.6 Treatment of Missing Data

All patients contributing at least one follow-up WOMAC Total score will be included in the primary superiority test through the use of the mixed model for repeated measures (MMRM) in the mITT analysis set. In this way patients with incomplete follow-up are retained and contribute to the primary superiority test.

As noted elsewhere, FDA has previously recommended to not include many baseline covariates in the MMRM due to the modest sample size. Therefore, the only baseline covariates available for implicit imputation of changes from baseline to Month 6 (180 days) is the baseline value itself and treatment group. It follows then, that for the ITT analysis, the MMRM will implicitly impute missing changes from baseline to Month 6

(180 days) for patients with no follow-up data as the within treatment group mean change score modified by the effect of the baseline value

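### The code for the primary test uses maximum likelihood with no small-sample correction: with equal SDs in the two arms, the 1-sided type 1 error is about 0.027 rather than 0.025 (minor)

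*Combined protocol and SAP*

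**What the plan says.** Section 8.3.1 says that "all MMRM parameters will be estimated using SAS PROC MIXED" and describes the model as a direct likelihood approach. Section 8.3.3 gives the code for the primary test. It begins "proc mixed data=dataset method=ml", has the model line "model womac_pain = trt time trt*time womac_pain_bl / s chisq", and uses an unstructured covariance over the 2, 3 and 6 month visits. No ddfm option is given. On where to read the result, the section says "The key results is listed among the results provided by the 'slice' option of the LSMEANS statement". It then commits to more than a p-value: "The Month 6 treatment group contrast, the p-value associated with the null hypotheses and 95% two-sided confidence interval will be derived from the MMRM".

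The success criterion in the protocol summary and section 3.2.2 is a 1-sided p of at most 0.025. Section 8.2 makes the Function test depend on it: "Formal testing of the conditional endpoint will only take place if the null hypothesis involving the primary endpoint is rejected at 1-sided alpha=0.025". Section 8.4.1 plans 60 ACP and 30 control patients.

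**The concern.** ML divides residual sums of squares by the number of patients and makes no allowance for the mean parameters that were estimated. Here there are 7: three visit means, three treatment differences and one common baseline slope. The variance estimate is then too small, and so is the standard error of the Month 6 contrast. REML makes the allowance. It is also likelihood-based and valid under the missing-at-random assumption in section 8.3.3, so the plan's rationale does not require ML.

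The p-value from this model decides study success and opens the second labeling claim. The hierarchy controls type 1 error only if each test holds its own level.

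**Working it through.** **Plan's own figure.** Effect size 0.80, 1-sided alpha 0.025, 2:1 allocation, two-sample t-test (section 8.4.1). Noncentral t power is 0.897 at 50/25 and 0.908 at 52/26, so N=78 for 90% power reproduces. 78 × 1.15 = 89.7, rounded to 90.

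**Closed form, equal SDs.** The ratio of the ML to the REML standard error is roughly sqrt((n − p)/n), with n = 90 and p = 2 to 3 mean parameters per visit (the baseline slope is shared over three visits).
- p = 2: sqrt(88/90) = 0.989. p = 3: sqrt(87/90) = 0.983.
- The code names no df method. Assume the between-subject df, 90 − 3 = 87 (intercept, treatment, baseline). The critical value is 1.988.
- 1-sided level = P(t87 > ratio × 1.988): 0.0263 at 0.989, 0.0267 at 0.985, 0.0270 at 0.983.

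**Simulation of the coded model.** ML and REML were fitted to the same data: normal errors, SD 3.4 in both arms (section 8.4.1), 200,000 null trials per scenario, both tails averaged, Monte Carlo SE 0.00024. The documents give no visit correlations. The adjacent-visit and 2-to-6-month correlations were therefore assumed at 0.4/0.3, 0.7/0.5 and 0.85/0.75. Missing Month 6 values were missing completely at random.

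| 60/30 | SE ratio ML/REML | ML level | REML level |
|---|---|---|---|
| Complete | 0.986, 0.985, 0.984 | 0.0266, 0.0267, 0.0270 | 0.0249, 0.0251, 0.0251 |
| 8 of 90 missing Month 6 | 0.985, 0.984, 0.984 | 0.0271, 0.0269, 0.0266 | 0.0253, 0.0251, 0.0250 |
| 13 of 90 missing Month 6 | 0.984, 0.984, 0.984 | 0.0278, 0.0273, 0.0271 | 0.0260, 0.0253, 0.0252 |

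The last row is 13/90 = 14%, close to the 15% allowance. Patients who miss Month 6 but have an earlier score stay in the model: "All patients contributing at least one follow-up WOMAC Total score will be included in the primary superiority test".

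- Lowest ML coverage: 1 − 2 × 0.02776 = 94.4%. Highest: 1 − 2 × 0.0266 = 94.7%.
- An independent simulation gave ML 0.0265 to 0.0266 with complete data and 0.0274 with 15% dropout. REML gave 0.0248 to 0.0251 and 0.0257.
- If the statistic is referred to a normal or chi-square distribution instead of t, ML gives 0.028 to 0.029 and REML 0.026 to 0.027.
- ML and REML verdicts differ in 0.16% to 0.20% of null trials. At effect 0.80 with complete data (low and middle correlation) they differ in 0.32% and 0.37%. Power there is 94.5% and 94.3% for ML, and 94.1% and 94.0% for REML.

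**Unequal SDs.** The code fits one covariance matrix for both arms. With 2:1 allocation, the pooled standard error is wrong if the SDs differ.
- Pilot Pain SDs 3.6 and 3.2 (section 8.4.1). Pooled variance (59 × 12.96 + 29 × 10.24)/88 = 12.06. Pooled SE sqrt(12.06 × (1/60 + 1/30)) = 0.777. True SE sqrt(12.96/60 + 10.24/30) = 0.747. Ratio 1.040, so the REML level is P(t87 > 1.040 × 1.988) = 0.021. For ML, 1.040 × 0.985 = 1.025, and the level is 0.022. Simulations gave ML about 0.022 to 0.023 and REML about 0.021 to 0.022.
- Pilot Function SDs 11.7 and 12.0 (section 8.4.2). Pooled variance 139.2, pooled SE 2.638, true SE sqrt(136.9/60 + 144/30) = 2.661, ratio 0.9915. For ML, 0.9915 × 0.985 = 0.977, and the level is about 0.0277. Simulations gave about 0.026 to 0.028.

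**The case against.** The strongest objection is that the direction of the level error depends on an assumption. A reader might infer that the test is always too liberal. The documents do not support that: with the pilot Pain SDs, the primary test stays below 0.025 even under ML. This stands, and it removes any claim of certain inflation. It does not justify ML. The pilot had 15 patients per arm, and a variance ratio of (3.6/3.2)² = 1.27 does not establish that the SDs differ. The power calculation itself uses a common SD of 3.4, and the Function SDs point slightly the other way. The level should not depend on one bias offsetting another.

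Second, REML alone is not a full repair. It leaves up to 0.026 with 13 of 90 missing. That stands, and the fix allows for it.

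Third, the practical effect is very small: only a p-value just under 0.025 could change. That stands too and sets the severity.

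A reader might also infer from the SLICE sentence that the plan cannot produce a signed contrast or an interval, or from the chisq option that the primary p-value is a chi-square one. Neither follows. A slice is an unsigned F-test without an interval, but section 8.3.3 commits to the contrast and its 95% interval. The text points to the slice result, not to a chi-square statistic. What is missing is a line of code that requests the contrast directly.

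**Conclusion.** The concern holds as a minor technical point. ML makes the Month 6 standard error about 1.5% smaller than REML at 60/30, and this hardly depends on visit correlation or missingness. If the arms have equal SDs, the 1-sided level is about 0.027 with complete data and up to about 0.028 with 13 of 90 missing, an excess over REML of 0.0017 to 0.0019. If the ACP arm has the larger SD, as in the pilot Pain data, the test is conservative and the ML bias is more than offset.

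The figures rest on normal errors, 87 df, the assumed correlations and Month 6 values missing completely at random. A reader might conclude that the sample size or the testing hierarchy is unsound. The documents do not support that: N=78 and N=90 reproduce, and the hierarchy itself is correct.

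**What to change.** In section 8.3.3:
- Replace method=ml with method=reml, and add ddfm=kr to the MODEL statement. Kenward-Roger is the standard small-sample adjustment when some Month 6 values are missing. It was not simulated here.
- State that the primary p-value comes from the resulting t or F test, not from a chi-square statistic.
- Request the Month 6 ACP-minus-control contrast and its 95% interval directly, with an ESTIMATE statement or LSMEANS trt*time / diff cl.

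Cost: the interval becomes about 1.5% to 1.7% wider (1/0.9856 = 1.015; 1/0.9836 = 1.017), and power at effect 0.80 falls by 0.3 to 0.4 points. N does not change. REML does not address unequal SDs: with the pilot Pain SDs it makes the test slightly more conservative. The edit is to protocol text, so it needs the sponsor, FDA and IRB approvals in section 9.16. It is best combined with another amendment and made before unblinding.
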